For Group 3: Subjects with previously treated, unresectable stage III or IV cancers of the head and neck with documented HER3 expression on the cell surface of the tumor ($\geq 1+$) and NRG1 expression using analytically validated assays by central laboratory.

- Subjects must have no more than 3 prior lines of systemic therapy and have disease progression on or after last prior treatment (based on RECIST v1.1).
- Subjects with locoregional recurrences amenable to resection/surgery or additional radiation are excluded.

For Group 4: Subjects with previously treated, unresectable stage III or IV NSCLC with documented HER3 expression on the cell surface of the tumor ($\geq 1+$) and NRG1 expression using analytically validated assays by central laboratory.

- Subjects must have no more than 3 prior lines of systemic therapy and have disease progression on or after last prior treatment (based on RECIST v1.1).
- Subjects with anaplastic lymphoma kinase (ALK) translocation who already received or were intolerant of prior anti-ALK therapy may be included.
- Subjects with EGFR mutation positive disease (e.g., exon 19 deletion and exon 21 L858R) who already received or were intolerant of prior EGFR inhibitors may be included.

Additional tumor histology groups predicted to be sensitive to the study drug based on biomarkers (e.g., HER3 mutations, NRG translocations) supported by preclinical or clinical data may be added based on emerging

data.

10. Subjects must have at least one measurable lesion per RECIST v1.1.

NOTE: If the only site of measurable disease has been previously irradiated, documented progression of disease and a 4-week interval since completion of radiotherapy is required.

NOTE: In subjects with ≥ 1 measurable lesion, a measurable lesion may be biopsied at Screening and Day 15; however that lesion must not be selected as a target lesion for disease assessment.

11. Subjects must have disease amendable to biopsy using a procedure that is safe for the subject, and agree to undergo pre- and on-treatment tumor biopsies (until the participating centers receive written notification from the Sponsor that paired tumor biopsies are no longer required).

Screening Exclusion Criteria for Parts 1 and 2

Subjects meeting any of the following criteria must not be enrolled in the study:

1. Subjects with leptomeningeal or brain metastases or spinal cord compression.

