3.4. Part 2: Molecularly-Defined Tumor Histology Groups

Part 2 can begin once the recommended dose and schedule is identified in Part 1. It is possible that more than one dose and/or schedule will be evaluated in Part 2 if available PK, PD and safety data suggest that multiple doses and schedules have desirable biologic activity or if an MTD cannot be established.

The selected dose level(s) will be evaluated in Part 2 for confirmation of safety and tolerability, as well as preliminary assessment of clinical benefit, in at least 4 molecularly-defined tumor histology groups of subjects with HER3 or HER3 and NRG1 expressing tumors. Group 1 will include subjects with HER3- expressing melanoma. Group 2 will include subjects with HER3-expressing gastric cancer. Group 3 will include subjects with HER3 expressing and NRG1-expressing cancers of the head and neck. Group 4 will include subjects with HER3 expressing and NRG1-expressing NSCLC. All subjects must have archival tissue available for HER3 and if required NRG1 testing or be willing to undergo a tumor biopsy using a procedure that is safe for the subject, to provide a sample for testing.

Each group will initially enroll 12 subjects with the option of expanding to a maximum of 30 subjects if futility criteria are not met using well established methodology of [Lee, 2008] (See Section 13.2.2 and Section 13.6.2 for additional details).

Subjects will be required to have disease amenable to biopsy and agree to pre-and on-treatment tumor biopsies, using a procedure that is safe for the subject. Pre-and on-treatment biopsies are mandatory for all subjects in all groups. GSK will closely monitor and evaluate the collection of evaluable biopsies and will notify the participating centers of any change to the collection requirements for any or all groups.

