- Subjects with EGFR mutations (e.g., exon 19 deletion and exon 21 L858R) who have documented progression (based on RECIST 1.1) or who were intolerant of prior EGFR inhibitors may be included.

Additional tumor histology groups predicted to be sensitive to the study drug based on biomarkers (e.g., HER3 mutations, NRG translocations) supported by preclinical or clinical data may be added based on emerging data.

10. Subjects must have at least one measurable lesion per RECIST v1.1.

NOTE: If the only site of measurable disease has been previously irradiated, documented progression of disease and a 4-week interval since completion of radiotherapy is required.

NOTE: In subjects with >1 measurable lesion, a measurable lesion may be biopsied at Screening and Day 15; however that lesion must not be selected as a target lesion for disease assessment.

11. Subjects must have disease amenable to biopsy and agree to undergo pre- and on-treatment tumor biopsies using a procedure that is safe for the subject (until the participating centers receive written notification from the Sponsor that paired tumor biopsies are no longer required).

5.2.5. Screening Exclusion Criteria for Parts 1 and 2

Subjects meeting any of the following criteria must not be enrolled in the study:

1. Subjects with leptomeningeal or brain metastases or spinal cord compression.
 - Subjects with untreated brain or meningeal metastases are not eligible (computed tomography [CT] scans are not required to rule this out unless there is a clinical suspicion of central nervous system [CNS] disease).
 - Subjects with treated and radiologic or clinical evidence of stable brain metastases (confirmed by 2 scans at least 4 weeks apart), with no evidence of cavitation or hemorrhage in the brain lesion are eligible providing that they are asymptomatic and do not require corticosteroids. Subjects are not permitted to receive enzyme inducing anti-epileptic drugs.
2. Prior HER3- directed treatment (HER2- or EGFR-directed treatment is acceptable).
3. Use of an investigational anti-cancer drug within 28 days (or 5 half-lives, whichever is longer) preceding the first dose of GSK2849330 OR chemotherapy within the last 3 weeks (6 weeks for prior nitrosourea or mitomycin C) OR any major surgery, radiotherapy, immunotherapy or any other anti-cancer therapy within the last 4 weeks, except as noted above.

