GSK2849330 IV infusion ¹⁵			X	X ²²	X	X ²²	X	Everyweek ^{15,22}		
AE assessment			Continuous							
Serum sample for Immunogenicity			X pre-dose						X ¹⁶	X ¹⁶
PGx sample			X pre-dose ¹⁷							
Tumor markers ¹⁸			X					Every 8 weeks		
Disease assessment ¹⁹		X ³						Every 8 weeks	X ²¹	

1. The Follow-up visit should be approximately 28 days after the last dose of study treatment.
2. The Post-study visit should be at least 45 days or 5 half-lives (whichever is longer) after the last dose of study treatment.
3. Within 14 days prior to first dose except for pregnancy test (7 days) and Disease Assessment within 28 days prior to the first dose.
4. Separate pre-screening consent required for fresh biopsy and fresh biopsy is only collected at pre-screening if archived tissue is not available.
5. Fresh pre- and on-treatment tumor biopsy is required; if adequate fresh biopsy tumor tissue is acquired during pre-screening, then this does not need to be repeated during the screening period. Archival tumor tissue is not acceptable to serve as pre-treatment tumor tissue.
6. Tumor biopsy is required on Day 15. Biopsy must be collected prior to study treatment administration on Day 15 dose (pre-dose).
7. Collected at progression. Tumor biopsy is optional and only collected from subjects with disease progression on study treatment. The tumor specimen may be collected at any time after study treatment discontinuation, but must occur prior to start of any subsequent anticancer therapy.

8. Perform only in women of child-bearing potential. Serum pregnancy test should be conducted at the Screening, Follow-up, and Post-study visits. Urine pregnancy test should be conducted pre-dose on Day 29 and every 4 weeks from Day 29 in the continuation phase of the study.
9. If the screening visit was completed within 72 hours of the first dose, this assessment does not need to be repeated on Day 1.
10. For vitals: collect at pre-dose and at 1, 2, 4, and 6 hours after the start of the first infusion. For ECG: collect at pre-dose and 2 hours after the start of the first infusion
11. ECHO is preferred; however, if echocardiography is not available, or if reliable echocardiographic analysis of LVEF is unable to be obtained due to technical factors, a MUGA scan may be performed. Regardless, the method used at Baseline should be used for the remaining assessments in the study. Assessments should be performed more frequently than every 8 weeks if clinically indicated.

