- PD: At least a 20% increase in the sum of the diameters of target lesions, taking as a reference, the smallest sum of diameters recorded since the treatment started (e.g., percent change from nadir, where nadir is defined as the smallest sum of diameters recorded since treatment start). In addition, the sum must have an absolute increase from nadir of 5 mm.
- Not Applicable (NA): No target lesions at baseline.
- Not Evaluable (NE): Cannot be classified by one of the five preceding definitions.

NOTE:

- If lymph nodes are documented as target lesions the short axis is added into the sum of the diameters (e.g., sum of diameters is the sum of the longest diameters for non-nodal lesions and the short axis for nodal lesions). When lymph nodes decrease to non-pathological size (short axis <10 mm) they should still have a measurement reported in order not to overstate progression.
- If at a given assessment time point all target lesions identified at baseline are not assessed, sum of the diameters cannot be calculated for purposes of assessing CR, PR, or SD, or for use as the nadir for future assessments. However, the sum of the diameters of the assessed lesions and the percent change from nadir should be calculated to ensure that progression has not been documented. If an assessment of PD cannot be made, the response assessment should be NE.
- All lesions (nodal and non-nodal) should have their measurements recorded even when very small (e.g., 2 mm). If lesions are present but too small to measure, 5 mm should be recorded and should contribute to the sum of the diameters, unless it is likely that the lesion has disappeared in which case 0 mm should be reported.
- If a lesion disappears and reappears at a subsequent time point it should continue to be measured. The response at the time when the lesion reappears will depend upon the status of the other lesions. For example, if the disease had reached a CR status then PD would be documented at the time of reappearance. However, if the response status was PR or SD, the diameter of the reappearing lesion should be added to the remaining diameters and response determined based on percent change from baseline and percent change from nadir.

Evaluation of non-target lesions

Definitions for assessment of response for non-target lesions are as follows:

- CR: The disappearance of all non-target lesions. All lymph nodes identified as a site of disease at baseline must be non-pathological (e.g., <10 mm short axis).

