# 9. DATA HANDLING CONVENTIONS

### 9.1. **Premature Withdrawal and Missing Data**

All subjects who withdraw prematurely from the study or investigational drug will be documented with the reason for their withdrawal recorded in the final Clinical Pharmacology Study Report (CPSR). All available data from subjects who withdraw will be listed and all available planned data will be included in the summaries according to the populations defined in Section 6.

In the event that the study is prematurely discontinued, all available data will be listed and a review will be carried out by the study team to assess which statistical analyses are still considered appropriate.

Missing data occurs when any requested data are not provided, leading to blank fields on the collection instrument. Those data will be indicated by the use of a "blank" in subject listing displays. Answers such as "Not applicable" and "Not evaluable" are not considered to be missing data and should be displayed as such.

Because the length of treatment for each subject will depend on the efficacy and toxicity of the treatment, the duration of treatment will vary across subjects. Similarly the duration of follow up will also vary. All available safety, and efficacy data will be analyzed using suitable statistical methods; subjects with shorter treatment and follow-up due to the natural history of their disease or medical necessities of the treatment of their disease will not be considered to have missing data. For endpoints which determine the percentage of responders, subjects with unknown/not evaluable or missing best overall response will be assumed to be non-responders, and will be included in the denominator when calculating the percentages.

Subjects with the designation of treatment relationship for adverse events (AE)s and serious adverse events (SAEs) missing will have the worst case assumed to impute the relationship: if relationship to study treatment is missing it will be assumed to be "Yes". There will be no other imputation for missing data other than what's described in Section 9.2 for partial dates and for missing exposure end dates.

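### The synopsis and Section 5.2.4 set different conditions for biopsying a measurable lesion, and under the synopsis wording a Part 2 subject with only one can be left unable to score a partial response

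*Protocol*

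**What the plan says.** Part 2 inclusion criterion 10 appears twice in the current protocol, in the synopsis and in Section 5.2.4. Both versions set the same entry requirement: "Subjects must have at least one measurable lesion per RECIST v1.1". One measurable lesion is therefore enough to enrol.

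A note on biopsies follows in each place, and the two notes differ in one symbol.

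- Synopsis: "In subjects with ≥ 1 measurable lesion, a measurable lesion may be biopsied at Screening and Day 15".
- Section 5.2.4: "In subjects with >1 measurable lesion, a measurable lesion may be biopsied at Screening and Day 15".

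Both notes then add the same restriction: "however that lesion must not be selected as a target lesion for disease assessment".

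Section 3.4 makes paired biopsies compulsory: "Pre-and on-treatment biopsies are mandatory for all subjects in all groups". The Part 2 Time and Events table (Table 12, footnotes) repeats this for the on-treatment sample, "Tumor biopsy is required on Day 15", and does not accept archival tissue as the pre-treatment sample. The sponsor may change the collection requirement for groups by notice to the centers (Section 3.4) or announce that pairs are no longer needed (criterion 11).

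The synopsis (clinical activity assessment) and Section 7.8 base the Part 2 futility decision on RECIST 1.1. Appendix 5 defines a partial response (PR) by the change in the summed diameters of target lesions.

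**The concern.** The two notes agree for a subject with two or more measurable lesions: one may be sampled and another followed. They part company for the subject with exactly one, whom both versions admit.

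Under the synopsis wording, that one lesion may be sampled and is then disqualified as a target. The subject was enrolled for having measurable disease but has no target lesion on which a PR could be measured. Under Section 5.2.4 the permission does not extend to this subject, but the text does not say what to do instead, and the biopsy requirement still applies.

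Each group faces its first futility comparison at 12 subjects and needs five responders out of 30 to pass. Subjects who cannot register a PR whatever the drug does push the observed response rate down and make a futility stop more likely. Which rule applies depends on which section the site reads.

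**Working it through.** **Tracing the single-lesion subject through Appendix 5 (synopsis wording)**

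1. The only measurable lesion is biopsied, so it cannot be a target lesion.
2. Target-lesion response becomes not applicable, which Appendix 5 describes as "No target lesions at baseline".
3. PR needs at least a 30% fall in the sum of target-lesion diameters. With no target lesion there is no sum.
4. Table 17 (measurable disease at baseline) has no row for a target response of not applicable. Table 18 is written for subjects with non-measurable disease only, so using it here is an inference. Its outcomes are complete response (CR), non-CR/non-PD, not evaluable and progression, with no PR.
5. CR through non-target lesions therefore remains possible and PR does not.
6. If best response ends as not evaluable, SAP Section 9.1 applies: "subjects with unknown/not evaluable or missing best overall response will be assumed to be non-responders", with the subject kept in the denominator. That sentence does not cover non-CR/non-PD, but such a subject is not a responder either.

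**Reproducing the design**

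Inputs (Protocol Sections 13.2.2 and 13.6.2): null rate 10%, alternative 30%, prior Beta(0.2, 0.8), 12 to 30 subjects. Success is a posterior probability of at least 0.80 that the rate exceeds 10%. Futility is a predictive probability of success below 0.06.

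- Posterior after x responders in 30 is Beta(0.2 + x, 0.8 + 30 − x). The probability that the rate exceeds 0.10 is 0.689 at x = 4 and 0.851 at x = 5, so success needs at least 5 of 30.
- Predictive probability uses the beta-binomial for the remaining 30 − n subjects. With 0 responders at n = 12 it is 0.0056. With 1 responder it is 0.0678 at n = 15 and 0.0502 at n = 16. With 2 it is 0.0819 at n = 21 and 0.0568 at n = 22. With 3 it is 0.0831 at n = 26 and 0.0439 at n = 27. This is the Table 15 boundary.
- Exact enumeration over all binomial paths gives the following.

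| Quantity | Stated | Computed |
|---|---|---|
| Type I error | 0.15 | 0.1486 |
| Power at 30% | 94% | 0.9445 |
| Early termination, null / alternative | 77% / 5% | 0.767 / 0.0455 |
| Expected size, null / alternative | 20 / 29 | 20.05 / 29.43 |

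The plan's figures are correct.

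**Sensitivity**

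Let f be the share of subjects who cannot register a PR. If all responses are PRs, response is unrelated to having a single lesion, and nobody is replaced, the observable rate is p × (1 − f). At a true rate of 0.30:

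| f | Observable rate | Power | Early futility stop |
|---|---|---|---|
| 0 | 0.300 | 0.9445 | 0.0455 |
| 5% | 0.285 | 0.9254 | 0.0606 |
| 10% | 0.270 | 0.9007 | 0.0799 |
| 20% | 0.240 | 0.8306 | 0.1349 |
| 30% | 0.210 | 0.7269 | 0.2177 |

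At a true rate of 10%, the chance of passing falls from 0.1486 to 0.1072, 0.0728 and 0.0457 for f = 10%, 20% and 30%. The distortion works only against a positive result.

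The values of f are assumptions, because the documents give none. f is the share with exactly one measurable lesion multiplied by the fraction of those whose lesion is actually the one sampled. If 20% have one lesion and half of those are sampled there, f is 0.20 × 0.50 = 10%.

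**The case against.** **A slip of one symbol.** Since criterion 10 already requires one measurable lesion, a note for one or more would cover everyone and its opening condition would do nothing. The greater-than sign in Section 5.2.4 makes better sense. The synopsis symbol may be a typing error, or an underlined sign misread when the PDF was converted. This is plausible and quickly checked in the source file. As it reads, however, the synopsis is current text stating an operative rule, and it differs from Section 5.2.4.

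**The note only permits.** Neither version requires the sample to come from a measurable lesion. A site may use another accessible site, and the sole lesion is lost only if it is chosen. Section 5.1 also allows replacement of Part 2 subjects for futility testing, and the sponsor can lift the biopsy requirement. All of this stands, and it is why the power figures are upper bounds.

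**Limited consequence.** Safety is the primary endpoint of Part 2 and response is secondary. SAP Section 11 abbreviates the efficacy analyses because the study stopped early. This lowers the weight of the point, but response still governs the futility rule and is still summarised.

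**A stronger reading that the documents do not support.** A reader might infer that Section 5.2.4 leaves sites free to sample the sole target lesion, so that tissue removal could itself produce a measured response. The permission there is conditional on having more than one measurable lesion, which implicitly leaves a sole lesion outside it. The documents give no effect of biopsy on lesion diameter, and a PR must be confirmed at least four weeks later. The fair criticism of Section 5.2.4 is only that the single-lesion case is left unstated.

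**Conclusion.** The point holds as a contradiction between two current versions of one eligibility criterion. Under the synopsis version, a subject whose only measurable lesion is biopsied has no target lesion and cannot be scored as a PR. Section 5.2.4 does not produce that result but does not say how the subject is handled while paired biopsies remain compulsory.

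The size is unknown. A loss of 4.4, 11.4 or 21.8 percentage points of power (94.45 minus 90.07, 83.06 or 72.69) is the most that would follow from 10%, 20% or 30% of subjects losing the chance of a PR, with every response a PR and no replacement. A reader might take the 73% figure as the expected power. It is not, because it needs 30% of subjects to have a single measurable lesion and every one of them to be sampled there. If the notes are reconciled so that every subject keeps an assessable target lesion, the stated 94% stands.

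**What to change.** Give the two notes the same condition. State in both how a subject with exactly one measurable lesion is handled, so that every response-evaluable subject keeps an assessable target lesion that is not the biopsied lesion. The detailed biopsy rule is for the sponsor to choose; what matters here is that the two places agree and cover this case.

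If the chosen rule means that some single-lesion subjects cannot supply paired samples, the protocol text must provide for that. It cannot be left to individual waivers: Section 3.1 does not allow them, and the sponsor's power in Section 3.4 and criterion 11 is a notice to centers about collection requirements, not a subject-level exemption.

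The cost is a wording change in two places and possibly a few lost paired biopsies. The futility boundary and the sample size do not change.

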1. INTRODUCTION

1.1. Background

Many tumor types are characterized by dysregulation of the human epidermal growth factor receptor (HER) family of tyrosine kinase receptors, which includes HER1 (EGFR), HER2 (ErbB2), HER3 (ErbB3), and HER4 (ErbB4) [Kolibaba, 1997]. Both EGFR and HER2 are established pharmacologic targets in the treatment of cancer; emerging evidence also suggests that HER3 is an important therapeutic target. HER3 is expressed in a broad range of solid tumors, with varying prevalence depending on primary tumor type and histology. HER3 is a potent mediator of downstream signaling when heterodimerized with other receptor tyrosine kinases (RTK). The heterodimerization partners include other HER family members, such as EGFR, HER2, and HER4, as well as other RTK classes, including cMET and IGF-1R. Intracellular tyrosine sites on HER3 can be phosphorylated by an activated partner protein allowing recruitment of adaptor proteins and downstream activation of the MAPK and AKT signaling pathways.

While the HER3 gene is not frequently amplified in human cancers, HER3 protein expression has been associated with aggressive histopathological characteristics and poorer survival in various tumor types including melanoma, ovarian, gastric and colorectal carcinomas [Reschke, 2008; Tanner, 2006; Hayashi, 2008; Beji, 2011]. In melanoma cases with high HER3 expression as determined by immunohistochemistry (IHC), the probability of tumor-related death was almost three times higher than in cases with low HER3 staining [Reschke, 2008]. In gastric cancer, HER3 overexpression was associated with a significantly worse survival ($P = 0.0000$) and was an independent prognostic factor in a multivariate analysis (hazard ratio 2.382; $p = 0.048$) [Hayashi, 2008]. In a recent meta-analysis that included 12 clinical studies (3 colorectal cancer [CRC], 2 gastric cancer, 2 breast cancer, and 1 each for melanoma, ovarian cancer, head and neck cancer, pancreatic cancer, and cervical cancer) HER3 over-expression, as determined by immunohistochemistry (IHC), was significantly associated with poorer overall survival at both 3 and 5 years [Ocana, 2013]. Recently, somatic mutations of HER3 have been described in ~11% of screened gastric and colon cancers [Jaiswal, 2013]. These mutations promote oncogenic signaling in a ligand-independent manner *in vitro*, suggesting functional relevance, and provide a potential targeted population for clinical studies.

HER3 is also increasingly recognized as an important mediator of drug resistance following treatment with inhibitors of multiple key cancer pathways, including EGFR, HER2, IGF-1R, PI3K, RAF and MAPK [Amin, 2010; Zhang, 2014; Kugel, 2014]. This role has important implications for the potential utility of anti-HER3 therapeutics in combination with inhibitors of these pathways. The development of therapeutic agents targeting HER3, either as single agents or in combination with other anti-cancer agents, may provide clinical benefit for subjects with cancers exhibiting HER3 expression.

